19.4. Schedule of Events – Treatment Maintenance Period and Follow-up

Period:	Treatment Maintenance																			
Visit:	6	7	8	9	10	11	12	13	14	15	16	17	18	19	20	21	22			
Day:	8	15	22	29	43	57	71	99	127	155	183	211	239	267	295	323	351			
Symptom-Directed Physical Examination	X	X	X	X	X	X	X	X	X	X	X	X	X	X	X	X	X	X	X	X
Vital Signs ⁴	X	X	X	X	X	X	X	X	X	X	X	X	X	X	X	X	X	X	X	X
ECG					X						X									X
Hematology (Central Laboratory)	X	X	X	X	X	X	X	X	X	X	X	X	X	X	X	X	X	X	X	X
Chemistry and Haptoglobin (Central Laboratory)	X	X	X	X	X	X	X	X	X	X	X	X	X	X	X	X	X	X	X	X
Coagulation Testing (Central Laboratory)	X	X		X		X		X		X		X		X		X		X		X
Pregnancy Test (for WOCBP only)	X	X		X		X		X		X		X		X		X		X		X
Blood Research Sampling (Central Laboratory)	X	X		X		X		X		X		X		X		X		X		X
Urine Sample for Urinalysis (Central Laboratory)	X	X		X		X		X		X		X		X		X		X		X
Urine Research Sampling (Central Laboratory)	X	X		X		X		X		X		X		X		X		X		X
Study Drug Administration-SC ¹	X	X	X	X	X	X	X	X	X	X	X	X	X	X	X	X	X	X	X	X
PK Serum Sampling (Central Laboratory)	X	X		X	X		X		X		X		X		X		X		X	
PD Serum Sampling (Central Laboratory)	X	X		X	X		X		X		X		X		X		X		X	
ADA Serum Sampling (Central Laboratory)				X		X		X		X		X		X		X		X		X
Adverse Events	X	X	X	X	X	X	X	X	X	X	X	X	X	X	X	X	X	X	X	X
Concomitant Medications & Therapies	X	X	X	X	X	X	X	X	X	X	X	X	X	X	X	X	X	X	X	X
Dispense study drug and ancillary supplies to Subject for SC injection at home	X	X	X	X	X	X	X	X	X	X	X	X	X	X	X	X	X	X	X	X
Study Drug Reconciliation (returned vials)	X	X	X	X	X	X	X	X	X	X	X	X	X	X	X	X	X	X	X	X
Quality of Life (QoL) Assessment (EQ-5D-5L)	X		X				X					X					X			
Health Economic Data	X	X	X	X	X	X	X	X	X	X	X	X	X	X	X	X	X	X	X	X
Patient Diary ³	X	X	X	X	X	X	X	X	X	X	X	X	X	X	X	X	X	X	X	X
Telephone Follow-up									X ²											

CONFIDENTIAL

No use, disclosure or reproduction outside of Omeros without prior written authorization

Period:	Treatment Maintenance														Follow-Up	
	Visit:	23	24	25	26	27	28	29	30	31	32	33	34	35	36	
Day:	379	407	435	463	491	519	547	575	603	631	659	687	715	729	743	771
Symptom-Directed Physical Examination	X	X	X	X	X	X	X	X	X	X	X	X	X	X	X	X
Vital Signs ⁴	X	X	X	X	X	X	X	X	X	X	X	X	X	X	X	X
ECG								X							X	X
Hematology (Central Laboratory)	X	X	X	X	X	X	X	X	X	X	X	X	X	X	X	X
Chemistry and Haptoglobin (Central Laboratory)	X	X	X	X	X	X	X	X	X	X	X	X	X	X	X	X
Coagulation (Central Laboratory)		X			X			X			X			X		X
Pregnancy Test (for WOCBP only)		X			X			X			X			X		X
Blood Research Sampling (Central Laboratory)		X			X			X			X			X		X
Urine Sample for Urinalysis (Central Laboratory)		X			X			X			X			X		X
Urine Research Sampling (Central Laboratory)		X			X			X			X			X		X
Study Drug Administration-SC ¹	X	X	X	X	X	X	X	X	X	X	X	X	X	X	X	
PK Serum Sampling (Central Laboratory)		X		X		X		X		X		X		X		X
PD Serum Sampling (Central Laboratory)		X		X		X		X		X		X		X		X
ADA Serum Sampling (Central Laboratory)		X		X		X		X		X		X		X		X
Adverse Events	X	X	X	X	X	X	X	X	X	X	X	X	X	X	X	X
Concomitant Medications & Therapies	X	X	X	X	X	X	X	X	X	X	X	X	X	X	X	X
Dispense study drug and ancillary supplies to Subject for SC injection at home)	X	X	X	X	X	X	X	X	X	X	X	X	X	X		
Study Drug Reconciliation (returned vials)	X	X	X	X	X	X	X	X	X	X	X	X	X	X	X	
Quality of Life (QoL) Assessment (EQ-5D-5L)		X				X				X				X		X
Health Economic Data	X	X	X	X	X	X	X	X	X	X	X	X	X	X	X	X
Patient Diary ³	X	X	X	X	X	X	X	X	X	X	X	X	X	X	X	
Telephone Follow-up	X ²	X ²	X ²	X ²	X ²	X ²	X ²	X ²	X ²	X ²	X ²	X ²	X ²	X ²	X ²	

CONFIDENTIAL

No use, disclosure or reproduction outside of Omeros without prior written authorization

Treatment Maintenance Period and Follow-up Footnotes:

¹ SC dosing daily

² Occurs between monthly visits

³ The subject will be responsible for maintaining a daily patient diary that records if the appropriate study drug was self administered.
Subjects will bring the diary into each clinic visit for review by the clinic staff

⁴ If the subject is aged 17 or younger, the subject height should also be recorded at visits 16, 22, 28, and 34

CONFIDENTIAL

No use, disclosure or reproduction outside of Omeros without prior written authorization

19.5. Rescue Therapy Schedule

Period:	Rescue Therapy			
Day:	RT1	RT2	RT3	RT4 ¹
Symptom-Directed Physical Examination	X	X	X	X
Vital Signs	X ²	X	X	X
Hematology (Central Laboratory)	X ³			
Chemistry and Haptoglobin (Central Laboratory)	X ³			
Urinalysis	X			
Blood Research Sampling (Central Laboratory)	X ³			
Urine Research Sampling (Central Laboratory)	X ³			
Study Drug Administration-IV	X			
Study Drug Administration-SC	X	X	X	X
PK Serum Sampling (Central Laboratory)	X ⁴	X ⁵	X ⁵	X ⁵
PD Serum Sampling (Central Laboratory)	X ⁶			
ADA Serum Sampling (Central Laboratory)	X ³			
Adverse Events	X	X	X	X
Concomitant Medications & Therapies	X	X	X	X

CONFIDENTIAL

No use, disclosure or reproduction outside of Omeros without prior written authorization

Rescue Therapy Schedule Footnotes:

¹ If the subject has received the last dose of IV OMS721 Rescue Therapy the procedures at this visit will be performed. If the subject is continuing IV OMS721 Rescue Therapy the procedures on this day will not be performed, but the subject will have the procedures for RT1. RT 4 occurs only when the subject completes Rescue Therapy and resumes treatment maintenance

² Pre-dose, Post start of IV dosing: 15 minutes, 30 minutes, 1 hour

³ Pre-dose

⁴ Pre-dose, Post end of IV dosing: 5 minutes, 1 hour, 24 hours, 48 hours, and 72 hours for the first dose of IV OMS721 Rescue Therapy only. The 24-, 48- & 72-hour timepoint collections will be coordinated to be drawn prior to the daily SC dose. Blood collections for PK will be drawn at pre-dose and 1 hour post start of dosing for all subsequent IV OMS721 doses during a single aHUS relapse. If no dose of IV OMS721 Rescue Therapy is given on this day the only PK sample collected will be the 72-hour PK blood sample coordinated with the SC dose as described in footnote 7

⁵ Pre- SC dose and the time of the blood collection will be coordinated with the 24-, 48- & 72-hour PK blood samples following the Day 1 IV dose (see footnote 6) allowing a single blood sample to provide both the post-IV PK samples and the pre-SC dose PK samples

⁶ Pre- IV dose and 1 hour post start of IV dose

CONFIDENTIAL

No use, disclosure or reproduction outside of Omeros without prior written authorization

1. LIST OF ABBREVIATIONS

Table 1: List of Abbreviations

Abbreviation	Explanation
AE	Adverse event
aHUS	Atypical hemolytic uremic syndrome
BMI	Body mass index
BP	Blood pressure
ECG	Electrocardiogram
eGFR	Estimated glomerular filtration rate
Kg	Kilogram

Omeros Corporation

Statistical Analysis Plan (Abbreviated) - Protocol No. OMS721-HUS-002

2. INTRODUCTION

This abbreviated statistical analysis plan (SAP) is based on:

- Protocol No. OMS721-HUS-002, Amendment 01, dated 26 May 2017
- ICH guideline E9 (Statistical Principles for Clinical Trials)

OMS-721-HUS-002 was discontinued due before a meaningful number of patients could be enrolled. The purpose of this document is to provide guidance for the analyses that will be performed on the available data.

Omeros Corporation

Statistical Analysis Plan (Abbreviated) - Protocol No. OMS721-HUS-002

3. STUDY DESIGN

For a detailed description of the proposed methodology for OMS271-HUS-002, please refer to the study protocol.

The study procedures and assessments are presented in Section 10 of the same document.

Omeros Corporation

Statistical Analysis Plan (Abbreviated) - Protocol No. OMS721-HUS-002

4. ANALYZED OBJECTIVES

4.1. Primary Objective

The primary objective of this study was to evaluate the effect of OMS721 in subjects with aHUS on platelet count change from baseline. As a sufficient number of patients were not enrolled, data for the primary objective will be not analyzed.

4.2. Secondary Objective(s)

The secondary objectives of this study were to evaluate the effect of OMS721 in subjects with aHUS on a variety of parameters. Parameters that will be analyzed include:

- Safety as assessed by AEs, SAEs, vital signs, ECGs, physical examinations, and laboratory measures
- Serum creatinine change from baseline
- Serum LDH change from baseline
- Serum haptoglobin change from baseline

4.3. Exploratory Endpoints

Not applicable as the study was terminated due to incomplete recruitment.

Omeros Corporation

Statistical Analysis Plan (Abbreviated) - Protocol No. OMS721-HUS-002

5. DEFINITIONS AND CALCULATION ALGORITHMS

5.1. Calculations Using Dates

Age at informed consent is calculated as the integer part of (date of informed consent – date of birth)/365.25.

Duration of treatment (weeks) is defined as (last dose date – first dose date + 1)/7.

Study day is defined as

- Event Date – First Dose Date + 1 if the event date is on or after the first dose date
- Event Date – First Dose Date if the event date is before the first dose date

5.2. Baseline

Prior to the first OMS721 treatment, subjects had two platelet count samples collected. The second platelet count sample was collected between 1 and 4 hours following the first platelet count sample. These samples were sent to the central laboratory and the mean value was used as the baseline platelet count for analyses. Visit 1 and Visit 2 may be combined for plasma therapy-resistant subjects. If Visit 1 and Visit 2 are combined, laboratory measures collected for Visit 1 will serve as the laboratory measures for Visit 2 as well.

For all the other variables, the baseline value will be the last recorded value prior to the administration of the first dose of study treatment.

5.3. Day 1

Study Day 1 is defined as the first dose date of the study drug.

5.4. Visit Windows Relative to the First Dose of Study Treatment

No windows will be defined for this study. Data collected at scheduled post-baseline visits will be analyzed at the visit where the values were collected. Data collected at unscheduled post-baseline visits and early termination visits will be analyzed at the closest planned visit if data were not collected at one of the two planned visits adjacent to this unscheduled or early termination visit. For example, if a subject early terminated from the study at Visit 35, and ECG was collected at Visit 35, then the ECG parameters collected at Visit 35 will be analyzed at Visit 36.

5.5. Analysis Populations

5.5.1. Safety Analysis Set

All presented analysis will be done using the safety analysis set which includes all subjects who receive any amount of study treatment.

Omeros Corporation

Statistical Analysis Plan (Abbreviated) - Protocol No. OMS721-HUS-002

6. DATA PRESENTATIONS AND DATA MANAGEMENT

6.1. Data Presentations

The plan for tabular presentations and analysis of the data, in general, is divided into five categories:

1. Subject disposition using the safety analysis set.
2. Baseline and demographic profile using the safety analysis set.
3. Safety and tolerability using the safety analysis set.

6.2. Data Management

All statistical analyses will be performed using SAS version 9.4 or later (SAS Institute Inc., Cary, NC).

Omeros Corporation

Statistical Analysis Plan (Abbreviated) - Protocol No. OMS721-HUS-002

7. SUBJECT DISPOSITION

The number of subjects treated, completing the protocol specified duration of study drug, discontinuing study drug early, completing the study, and early withdrawal from the study will be summarized by cohort. The reason(s) for early discontinuation of study drug and early withdrawal from the study will be summarized. A list of subjects failing any eligibility criteria will be provided.

Omeros Corporation

Statistical Analysis Plan (Abbreviated) - Protocol No. OMS721-HUS-002

8. BASELINE SUBJECT DATA

8.1. Baseline Demographic and Subject Characteristics

The following demographic characteristics and baseline values will be summarized by cohort: Age at informed consent, gender, ethnicity, race, childbearing potential, weight, BMI, systolic blood pressure, diastolic blood pressure, duration of disease, history of kidney transplantation for aHUS, platelet count, serum lactate hydrogenase, serum creatinine, and eGFR.

Concomitant medications used at baseline will be listed.

8.2. Medical History and Physical Examination

Medical and surgical history, history of aHUS and comprehensive and symptom-directed physical examinations will be presented in listings.

Omeros Corporation

Statistical Analysis Plan (Abbreviated) - Protocol No. OMS721-HUS-002

9. EFFICACY ANALYSIS

9.1. General Considerations

This study was discontinued due to the inability to recruit a meaningful number of subjects; therefore, no efficacy analyses will be performed. Analyses that will be performed are outlined in this SAP.

Omeros Corporation

Statistical Analysis Plan (Abbreviated) - Protocol No. OMS721-HUS-002

10. SAFETY AND TOLERABILITY

10.1. Overall Summary of Safety

An overall summary of treatment-emergent adverse events, which is defined as the AEs occurring or worsening after the start of study treatment, will be provided by cohort. All AEs will be coded by MedDRA. The following items will be included in the overall summary:

- Subject incidence of treatment-emergent AEs
- Subject incidence of treatment-related AEs (defined as probable or possible related to study drug)
- Subject incidence of treatment-emergent AEs by maximum CTCAE grade
- Subject incidence of treatment-emergent serious AEs (SAEs)
- Subject incidence of treatment-emergent AEs leading to discontinuation of study drug
- Subject incidence of treatment-emergent AEs leading to discontinuation of study
- Subject incidence of treatment-emergent fatal AEs
- Total number of unique treatment-emergent AE MedDRA preferred terms
- Median number of unique treatment-emergent AE MedDRA preferred terms per subject
- Total number of unique treatment-emergent SAE MedDRA preferred terms
- Median number of unique treatment-emergent SAE MedDRA preferred terms per subject

10.2. Adverse Event Preferred Term and Body/Organ System Summary Tables

Subject incidence of the following treatment-emergent AEs will be provided by cohort:

- Pre-treatment AEs will be summarized by MedDRA SOC and preferred term (pre-treatment AEs are those AEs that occurred prior to the start of study treatment)
- treatment-emergent AEs by MedDRA SOC, and preferred term
- treatment-emergent AEs by MedDRA preferred term
- treatment-related AEs by MedDRA SOC, and preferred term
- treatment-emergent AEs by MedDRA preferred term, and maximum CTCAE grade
- AEs leading to study drug discontinuation by MedDRA SOC, and preferred term
- AEs leading to study discontinuation by MedDRA SOC, and preferred term
- treatment-emergent SAEs by MedDRA SOC, and preferred term
- treatment-related SAEs by MedDRA SOC, and preferred term

Omeros Corporation

Statistical Analysis Plan (Abbreviated) - Protocol No. OMS721-HUS-002

- AEs leading to death by MedDRA SOC, and preferred term

10.3. Study Treatment Adherence and Extent of Exposure

Intravenous doses of the study drug are to be administered by study personnel.

To ensure good treatment adherence for study drug administered subcutaneously, investigative site personnel has prepared and administered the first SC injection at Visit 2 to train the subject or subject's caregiver on the proper techniques for dose preparation and injection. During Visit 3 (Day 2), Visit 4 (Day 3), and Visit 5 (Day 4) investigative site personnel observed and ensured that the subject is trained on the proper way to prepare and administer OMS721 SC. If deemed necessary, the site continued to instruct and observe SC injections by subject or subject's caregiver after Visit 5 (Day 4).

The following exposure items will be summarized with descriptive statistics by route (IV and SC) and cohort using the safety analysis set:

- Cumulative doses in milligrams taken by treatment period (the Treatment Induction Period, the Treatment Maintenance Period and the entire treatment period).
- Duration of treatment in weeks by treatment period, which is defined as (the last dose date of the treatment period – the first dose date of the treatment period + 1)/7.

10.4. Concomitant and Other Medications

Subject incidence of concomitant medications will be provided by WHODrug preferred term and cohort.

10.5. Routine Laboratory Data

Summary statistics for actual values and for change from baseline will be tabulated as appropriate for laboratory results by scheduled visit and cohort. Subjects with laboratory values outside of the normal reference range at any post-baseline safety assessment will be listed by cohort.

Shifts from baseline laboratory values (normal/abnormal) will be tabulated by cohort.

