Subjects who remain thrombocytopenic despite plasma therapy as described above will enter screening. The screening visit is Visit 1. At screening, four sets of laboratory samples will be collected: the first two sets will include one set for analysis in the local laboratory to determine eligibility and the other set for analysis in the central laboratory to be used for efficacy and safety evaluations. Local laboratory measures will include at least platelet count, hemoglobin, LDH, creatinine, haptoglobin, schistocyte count, alanine transaminase (ALT), and aspartate transaminase (AST) to determine eligibility. The third and fourth sets of laboratory samples are platelet count only and will be drawn between 1 and 4 hours following the first and second sets: one set will be analyzed by the local laboratory to determine eligibility and the other set will be sent for analysis at the central laboratory. Eligibility will be determined by local laboratory measures. The platelet count used for eligibility will be the mean of the two screening platelet counts measured at the local laboratory.

Because some plasma therapy-resistant subjects may have severe or unstable aHUS when enrolled and certain laboratory tests can require several days for reporting, Investigators may initiate treatment with OMS721 prior to receiving the screening central laboratory results for the Shiga toxin assay, the human immunodeficiency virus (HIV) assay, and the ADAMTS13 assay. If a subject receives treatment prior to investigative site receipt of any of the Shiga toxin assay, the HIV assay, and the ADAMTS13 assay and any of those assays is subsequently found to be positive, the subject will be immediately discontinued from the study. This possibility that a subject may be withdrawn from OMS721 treatment following its initiation will be explained in the informed consent document.

Plasma Therapy-Responsive Cohort

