8. SELECTION AND WITHDRAWAL OF SUBJECTS

8.1. Subject Inclusion Criteria

Subjects may be included in the study only if they meet all of the following criteria:

1. Competent to provide informed consent or, if a minor, have at least one parent or legal guardian to provide informed consent with written assent from the subject.
2. If an adult, voluntarily provide informed consent in accordance with regulations and governing ethics committee requirements prior to any procedures or evaluations performed specifically for the sole purpose of the study. If a minor, at least one parent or legal guardian must provide informed consent and the subject must provide assent in accordance with local regulations and governing ethics committee requirements prior to any procedures or evaluations performed specifically for the sole purpose of the study.
3. Willing and able to comply with study procedures.
4. Are age ≥ 12 at screening (Visit 1).
5. Have a primary aHUS, diagnosed clinically, and have ADAMTS13 activity $> 5\%$ in plasma. Patients are eligible with or without a documented complement mutation or anti-CFH antibody. Patients are categorized according to their response to plasma therapy (plasma exchange or plasma infusion):
 - a. Plasma therapy-resistant aHUS patients must have all of the following:
 - i. Screening platelet count $< 150,000/\mu\text{L}$ despite at least 4 plasma therapy treatments in a 7-day prior to screening
 - ii. Evidence of microangiopathic hemolysis (at least one of: (1) presence of schistocytes, (2) serum LDH > 1.5 times upper limit of normal (ULN), and (3) haptoglobin $< \text{LLN}$)
 - iii. Serum creatinine $> \text{ULN}$

CONFIDENTIAL

No use, disclosure or reproduction outside of Omeros without prior written authorization

- b. Plasma therapy-responsive aHUS patients must have all of the following:
 - i. Have a documented history of requiring plasma therapy to prevent aHUS exacerbation defined as all of the following:
 1. decrease in platelet count > 25% when plasma therapy frequency has been decreased (including discontinuation of plasma therapy)
 2. LDH > 1.5 times ULN when plasma therapy frequency has been decreased (including discontinuation of plasma therapy)
 - ii. Have received plasma therapy at least once every 2 weeks at an unchanged frequency for at least 8 weeks before first dose of OMS721

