12.2.2. Definitions of Severity

Adverse events will be graded using the Common Terminology Criteria for Adverse Events (CTCAE) v.4.0 [USDHHS 2009].

Note that “seriousness” and “severity” are distinct concepts. “Serious” is a term applied to an AE that meets specific requirements (refer to Section 12.2.1). “Severity” refers to the AE intensity classification.

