13.2.13.4. Clinical Laboratory Results

Summary statistics for actual values and for change from baseline will be tabulated as appropriate for laboratory results by scheduled visit and cohort. Subjects with laboratory values outside of the normal reference range at any post-baseline assessment will be summarized.

Shifts from baseline laboratory values (normal/abnormal) will be tabulated.

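### The normal/abnormal laboratory shift table cannot separate worsening from no change in platelets and creatinine for nearly all plasma therapy-resistant subjects

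*SAP*

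**What the plan says.** The shift rule has two categories in both documents. SAP 10.5: "Shifts from baseline laboratory values (normal/abnormal) will be tabulated by cohort". Protocol 13.2.13.4: "Shifts from baseline laboratory values (normal/abnormal) will be tabulated". Neither gives direction (low or high) or grade. Neither says which post-baseline value is compared with baseline: the worst, the last, or the value at each visit.

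Protocol 8.1, criterion 5a, requires a resistant subject to have a screening platelet count below 150,000/µL and a serum creatinine above the upper limit of normal (ULN). Entry is judged on local values: "Eligibility will be determined by local laboratory measures" (protocol 7.1). The analysis baseline is a different measurement. For platelets, SAP 5.2 says "These samples were sent to the central laboratory and the mean value was used as the baseline platelet count for analyses". For the other tests, "the baseline value will be the last recorded value prior to the administration of the first dose of study treatment". Protocol 7.1 limits screening in this cohort to 5 days and allows Visits 1 and 2 to be combined.

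SAP 10.5 also plans summary statistics of actual values and of change from baseline by visit and cohort, and a listing of subjects with out-of-range post-baseline values. SAP 4.2 keeps creatinine, LDH and haptoglobin change from baseline. Platelet change is not in that list, and SAP 4.1 and 9.1 drop the primary objective and all efficacy analyses.

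**The concern.** A shift table is meant to show, subject by subject, who moved in a harmful direction. It does this poorly when the entry criteria place most subjects in the worst category it has. In the resistant cohort, platelets and creatinine are the two tests that criterion 5a requires to be abnormal, so for these tests the table can display normalization but can hardly display deterioration. A reader who sees only abnormal-to-abnormal and abnormal-to-normal counts could take the absence of adverse shifts as reassurance, although the format could not have shown them.

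The table matters more in the abbreviated SAP than it did in the protocol. TMA event-free status, whose definition includes the absence of a platelet fall of more than 25% from baseline (protocol 7.3.2), goes with the efficacy analyses. Platelet worsening is then left to the routine laboratory output and to adverse event reports.

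**Working it through.** The plan states no figure for this point, so there is none to reproduce. The check is the logic of the table, followed by a sensitivity calculation for how many resistant subjects could escape the abnormal row.

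**1. The cells.** For a subject with an abnormal baseline:

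| What happens after baseline | Cell |
|---|---|
| Returns to normal | abnormal to normal |
| Stays about the same | abnormal to abnormal |
| Gets worse in the same direction | abnormal to abnormal |
| Crosses from abnormally low to abnormally high, or the reverse | abnormal to abnormal |

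Take illustrative values: platelets falling from 120 to 15 ×10⁹/L, a change of 15 − 120 = −105, or a creatinine that rises fourfold. Either is counted together with a stable subject. The only cell that signals harm, normal to abnormal, is open only to subjects with a normal baseline.

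**2. Who can have a normal baseline?** There are two routes.

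- The local screening value and the analysis baseline can disagree, through measurement differences between laboratories or change over 0 to 5 days. This applies to both tests.
- For platelets, 150,000/µL is a fixed cut-off and is not tied to the laboratory's lower limit of normal (LLN). If the LLN is below 150, a count between the LLN and 150 is eligible and normal. Creatinine has no such gap, because its entry limit is the ULN itself.

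**3. How many, for platelets?** The documents give no entry distribution, measurement error or LLN, so these are assumptions: true count normal with mean 105 and SD 30 (×10⁹/L), independent local and central error with SD 0 to 20, and central LLN 130, 140 or 150. Change over the screening days is not modelled. With no error, the share normal at baseline among eligible subjects is

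[Φ((150 − 105)/30) − Φ((LLN − 105)/30)] / Φ((150 − 105)/30).

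For LLN 140 this is (0.9332 − 0.8783)/0.9332 = 5.9%. For LLN 130 it is (0.9332 − 0.7977)/0.9332 = 14.5%. With error, by simulation:

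| Central LLN | SD 0 | SD 5 | SD 10 | SD 15 | SD 20 |
|---|---|---|---|---|---|
| 150 | 0.0% | 1.4% | 2.7% | 4.4% | 6.3% |
| 140 | 5.9% | 6.1% | 7.4% | 9.2% | 11.3% |
| 130 | 14.5% | 14.6% | 15.3% | 16.8% | 18.5% |

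If every platelet count then halved, the table would show worsening only in the shares above. The remaining 100 − 18.5 = 81.5% to 100 − 0 = 100% would be counted as abnormal to abnormal.

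**4. What the other outputs show.**

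- Protocol 13.2.1 defines summary statistics for continuous variables to include minimum and maximum. Applied to change from baseline in SAP 10.5, the fall from 120 to 15 would give a minimum change of −105 or lower at that visit.
- SAP 5.4 moves unscheduled results to the closest planned visit only where adjacent planned data are missing. An extreme value at an unscheduled visit may therefore not enter those summaries.
- The out-of-range listing covers any post-baseline safety assessment, but in this cohort it will include subjects with stable and with worsening abnormality alike.
- SAP 10.2 tabulates adverse events by maximum CTCAE grade. Protocol 12.1 limits laboratory adverse events to clinically significant changes with symptoms or needing intervention, so an asymptomatic change may not appear.

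**The case against.** The strongest reply is that this is one table among several, in a study that has ended. Minimum and maximum change by visit expose an extreme fall or rise at a scheduled visit, so it is wrong to say that visit summaries hide it in a mean. The listing allows individual subjects to be followed if values are printed, creatinine change is kept as an analysis of its own, and clinically significant laboratory findings can enter the graded adverse event tables. SAP 2 says the study was discontinued before a meaningful number of patients was enrolled. With few subjects, a listing may serve as well as a shift table. CTCAE was adopted for adverse events (protocol 12.2.2), not for laboratory shifts.

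Most of this stands, and it sets the size of the point. It does not make the planned table informative: minimum and maximum show that someone worsened, not who or how many.

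A reader might go further and infer that every resistant subject is abnormal at baseline, so that the normal-to-abnormal count is zero by construction. The documents do not support that, because entry rests on local screening values and a fixed platelet cut-off, while the table uses a later or different measurement. A reader might also infer that the laboratory safety analysis as a whole is tilted in the drug's favour. That does not follow either, since the outputs above can show deterioration.

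**Conclusion.** The point holds for this table. For platelets and creatinine in the resistant cohort, the normal/abnormal shift can show recovery but cannot distinguish worsening from stability in nearly all subjects, and it merges low with high. The logic rests on criterion 5a and the two-category rule alone. The 0 to 18.5% of resistant subjects who might be normal at baseline for platelets rests on assumed inputs; no such figure was computed for creatinine.

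The scope is narrow. Responsive subjects may enter with normal markers (protocol 7.1), and there the table can show worsening. LDH and haptoglobin are affected only in part, because criterion 5a asks for at least one of three signs of hemolysis. The planned 56 resistant subjects among 80 (protocol 13.1) should not be used to size the problem, because the study stopped early; the SAP gives no enrolled number. The impact is small and the remedy is a cheap improvement.

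**What to change.** In SAP 10.5:

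- Replace the normal/abnormal shift with baseline category against worst post-baseline category. Use low/normal/high, or CTCAE v4.0 grade where one exists for the test, and show the low and high directions separately.
- State that the worst value is taken over all post-baseline results, and whether unscheduled visits are included.
- For platelets and creatinine, add each subject's worst post-baseline change from own baseline (lowest platelet count, highest creatinine).

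The grading scale is already in use: "Adverse events will be graded using the Common Terminology Criteria for Adverse Events (CTCAE) v.4.0" (protocol 12.2.2). Applying it to laboratory values is an extension that the SAP should state. Protocol 13.2.13.4 has the same two-category wording; the change can be made in the SAP and noted in the study report.

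The cost is SAP wording and one re-programmed table. No new data are needed.
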